SSO within 6 weeks was analyzed using logistic regression. Separate logistic regression models were fit for the RCT and for the observational cohort, with mesh type (XenMatrix vs. Strattice) as the primary predictor. Simple logistic regression and multivariable logistic regression was used for each study type (RCT and observational). Both models were adjusted by hernia width, CDC wound class, immunosuppression, and recurrent hernia to account for potential confounding in the observational group. Covariates were selected based on evidence in the literature as well as potential imbalance. The final number of covariates was limited to avoid model overfitting.

Confounders:

- Hernia width
- Wound class
- Immunosuppression
- Recurrent hernia

After obtaining separate estimates from the RCT and observational cohort, a random-effects meta-analysis was performed to derive a combined estimate. A combined estimate for the log odds ratio was calculated using inverse variance weighting and a restricted maximum likelihood estimator. Between-study heterogeneity was assessed by the I^2 measure.

Forest plots and summary tables for the log odds ratio and odds ratio were generated to summarize results.

Statistical and Study Design Considerations

Rationale for Combining RCT and Observational Study Data

- RCT was terminated early for difficulties with enrollment, resulting in very imbalanced group sizes.
- While some guidelines caution against combining observational studies with RCTs in a single meta-analysis due to methodological differences [2], other sources emphasize that in many situations, the benefits of incorporating all available evidence can outweigh the drawbacks, provided proper methods are used [2, 3]
- [3] proves a framework for synthesis of non-randomized and randomized studies.
 - In this study, the observational data come from the same single site as the RCT and are not subject to publication bias.

Choice of Statistical Methods

- Frequentist methods were chosen for broader audience familiarity. Although Bayesian multi-level models are an option, they can be sensitive to prior specification, and the intended audience may be less familiar with them.
- There are not enough events to perform analysis for other outcomes.
- Propensity score matching was not used because it can substantially reduce the sample size (i.e., discarding unmatched patients).

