SSO within 6 weeks : Yes	20	4/12 (33.33)	4/8 (50.00)	$\chi^2_1=0.56, P=0.46^2$
SSO Type (cata)				
Skin necrosis : Yes	20	0/12 (0.00)	1/8 (12.50)	$\chi^2_1=1.58, P=0.21^2$
Enterocutaneous fistula : Yes	20	2/12 (16.67)	0/8 (0.00)	$\chi^2_1=1.48, P=0.22^2$

Table 3b: 6-week outcomes, observational patients (*continued*)

Variables	N	Strattice	XenMatrix	Test Statistic
Dehiscence : Yes	20	2/12 (16.67)	0/8 (0.00)	$\chi^2_1=1.48$, P=0.22 ²
Seroma : Yes	20	1/12 (8.33)	0/8 (0.00)	$\chi^2_1=0.70$, P=0.40 ²
Hematoma : Yes	20	0/12 (0.00)	0/8 (0.00)	NA
Infection : Yes	20	1/12 (8.33)	3/8 (37.50)	$\chi^2_1=2.55$, P=0.11 ²
Mesh infection : Yes	19	0/11 (0.00)	0/8 (0.00)	NA

Note:

N is the number of non-missing value. 1 Kruskal-Wallis. 2 Pearson. 3 Wilcoxon.

Stat, P is the test statistic and p-value.

cata = check all that apply

Results

Executive Summary

Unadjusted Random Effects Meta-Analysis (Simple Logistic Regression):

Effect Estimate (Odds Ratio): 3.718 (0.897, 15.404)

Significance: The pooled estimate was not statistically significant.

Heterogeneity:

I^2 (total heterogeneity / total variability): 3.29%

H^2 (total variability / sampling variability): 1.03

Test for Heterogeneity:

$Q(df = 1) = 1.0340$, $p\text{-val} = 0.3092$

There appears to be minimal variability between the two studies. The I^2 value of 3.29% indicates that nearly all of the total variation can be explained by chance rather than true heterogeneity, and an H^2 of 1.03 reflects low excess variability. The Q test ($Q = 1.034$, $p = 0.3092$) is nonsignificant, confirming that there is no strong evidence of meaningful heterogeneity.

Adjusted Random Effects Meta-Analysis (Multivariable Logistic Regression):

Effect Estimate (Odds Ratio): 12.476 (1.745, 89.199)

Significance: The pooled estimate was statistically significant.

Heterogeneity:

I^2 (total heterogeneity / total variability): 0.00%

H^2 (total variability / sampling variability): 1.00

Test for Heterogeneity: $Q(df = 1) = 0.2830$, $p\text{-val} = 0.5947$

There is effectively no evidence of meaningful heterogeneity between the RCT and the observational study, provided by 0.00% I^2 value. Similarly, $H^2 = 1.00$ supports the absence of excess variability beyond what would be expected by sampling error alone. Finally, the Q test ($Q = 0.2830$, $p = 0.5947$) is non-significant, confirming that the studies are consistent and do not exhibit statistically detectable heterogeneity.

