When covariates were included in the model, a previously non-significant association between the exposure and outcome became statistically significant. This shift suggests that the unadjusted analysis may have been confounded—i.e., certain variables were masking or biasing the relationship.

Note

Be wary of exaggerated findings, as smaller studies are more prone to exaggeration. This is known as a Type M (magnitude) error. In other words, a finding must be large enough to exceed the statistical significance threshold despite wide confidence intervals, which systematically inflates the estimated effect size. Consequently, although we observed a strong effect, its true magnitude may be substantially lower than our point estimate suggests.

Gelman, A., & Carlin, J. (2014). Beyond Power Calculations: Assessing Type S (Sign) and Type M (Magnitude) Errors. *Perspectives on Psychological Science*, 9(6), 641-651.

[figure not shown]
Random Effects Meta-Analysis: Simple Logistic Regression

Simple logistic regression = logistic regression with no adjustment for confounders

[figure not shown]
Random Effects Meta-Analysis: Simple Logistic Regression

Study	Estimate (log OR)	95% CI (log OR)	Estimate (OR)	95% CI (OR)	P-value
Randomized	2.162	(0.365, 5.123)	8.684	(1.441, 167.853)	0.049
Observational	0.693	(-1.143, 2.597)	2.000	(0.319, 13.423)	0.459
RE Meta-Analysis	1.313	(-0.108, 2.735)	3.718	(0.897, 15.404)	0.070

Forest Plot: Log Odds Scale

Forest Plot: Odds Scale

[figure not shown]

Random Effects Meta-Analysis: Multivariable logistic regression

[figure not shown]
Random Effects Meta-Analysis: Multivariable Logistic Regression

Study	Estimate (log OR)	95% CI (log OR)	Estimate (OR)	95% CI (OR)	P-value
Randomized	2.968	(0.815, 6.261)	19.458	(2.258, 523.717)	0.023
Observational	1.882	(-0.898, 5.783)	6.569	(0.407, 324.629)	0.230
RE Meta-Analysis	2.524	(0.557, 4.491)	12.476	(1.745, 89.199)	0.012

Log Odds Scale

Odds Scale

FAQ

Q: What is overfitting?

A: Overfitting in regression happens when a model is too complex, often due to too many parameters relative to a small sample size, causing it to capture noise rather than the true data pattern. With limited data, the model lacks sufficient information to generalize well, leading to poor performance on new data because it is overly tailored to the specific quirks of the training set.

Q: What is a chunk (or composite) test?

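### Study-level P values and confidence intervals in the SAP come from different methods, and the unadjusted pooled result is borderline and method-dependent, so its change to significance after adjustment is not evidence of confounding

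*SAP*

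**What the plan says.** Under Primary Outcome Analysis, the SAP fits simple and multivariable logistic models for SSO within 6 weeks, separately in each source, and pools the two log odds ratios: "A combined estimate for the log odds ratio was calculated using inverse variance weighting and a restricted maximum likelihood estimator". It does not say which standard errors enter the weights, or how the study-level intervals and P values are obtained.

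The unadjusted results table gives the randomised patients an odds ratio of 8.684 ("1.441, 167.853"; log scale 0.365 to 5.123) with P = 0.049. The observational patients have 2.000 (log scale -1.143 to 2.597) with P = 0.459. The pooled row is 3.718 (0.897 to 15.404), P = 0.070, and the Executive Summary comments: "The pooled estimate was not statistically significant". The adjusted pooled odds ratio is 12.476 (1.745 to 89.199), P = 0.012, and is called significant. The Executive Summary then says of the difference: "This shift suggests that the unadjusted analysis may have been confounded".

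**The concern.** The randomised interval is far from symmetric around its log odds ratio of 2.162 (1.80 below, 2.96 above), so it is not the Wald interval that would go with a Wald P value. Its lower limit, an odds ratio of 1.44, is well clear of 1, yet the P value beside it only just passes 0.05. A reader cannot tell which inference the row reports.

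The second issue concerns interpretation. Randomised Strattice has one event, a setting in which Wald standard errors approximate poorly. The Executive Summary argues from the unadjusted pooled P lying above 0.05 and the adjusted P below it. If the first of these depends on the pooling method, the argument loses its premise.

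**Working it through.** **Inputs** (SAP Tables 3a and 3b, SSO within 6 weeks): randomised XenMatrix 11/30, Strattice 1/16; observational XenMatrix 4/8, Strattice 4/12. The SAP states no significance level. I use two-sided 5%, in line with its 95% intervals and with the alpha in the protocol's sample-size section.

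**1. Study rows.** Wald variance = 1/a + 1/b + 1/c + 1/d.
- Randomised: log OR = ln[(11 × 15)/(19 × 1)] = 2.1615. Variance = 1/11 + 1/19 + 1/1 + 1/15 = 1.2102, SE 1.100. z = 1.965, P = 0.0494, which is the printed P. Wald interval 2.1615 ± 1.96 × 1.1001 = 0.005 to 4.318, which is not the printed interval. The profile-likelihood interval is 0.365 to 5.123, as printed, and its likelihood-ratio P is 0.015.
- Observational: log OR = ln 2 = 0.6931. Variance = 1/4 + 1/4 + 1/4 + 1/8 = 0.875, SE 0.935, Wald P = 0.459 (printed). Profile interval -1.143 to 2.597 (printed).

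**2. The SAP's pooled figure, reproduced.** With two studies, REML gives τ² = [(2.1615 - 0.6931)² - (1.2102 + 0.875)]/2 = 0.035. Weights are 1/(1.2102 + 0.0354) = 0.803 and 1/(0.875 + 0.0354) = 1.098. Pooled log OR = (0.803 × 2.1615 + 1.098 × 0.6931)/1.901 = 1.313, SE = 1/√1.901 = 0.725. This gives OR 3.718 (0.897 to 15.40), P = 0.070, Q = 1.034 and I² = 3.29%, all matching the SAP. Standard errors taken from the printed interval widths do not match (OR 3.50, P 0.095, I² 0%). The pooling therefore used Wald standard errors.

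**3. Adjusted rows.** These cannot be refitted without patient data. Wald standard errors back-calculated from the printed P values (1.306 and 1.568) give OR 12.47 (1.745 to 89.1), P 0.012 and Q 0.283, which agree with the SAP to rounding. Standard errors from the printed interval widths give 12.6 (1.53 to 104), P 0.019, which do not agree. The same mix is therefore inferred in the adjusted table.

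**4. Other analyses of the same unadjusted counts.**

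| Method | OR (95% CI) | P |
|---|---|---|
| SAP two-stage REML | 3.72 (0.90 to 15.4) | 0.070 |
| Two-stage fixed effect, Wald SEs | 3.70 (0.92 to 15.0) | 0.066 |
| One-stage logistic, study intercepts, likelihood ratio | 4.09 (1.22 to 16.5) | 0.021 |
| Same model, Wald | 4.09 (1.14 to 14.7) | 0.031 |
| Random-slope logistic (between-study SD estimated at 0), likelihood ratio | 4.09 | 0.032 |
| Exact conditional | 1.007 to 18.6 | 0.0485 to 0.0493 |
| Cochran-Mantel-Haenszel, uncorrected | 4.28 (1.14 to 16.1) | 0.028 |
| Cochran-Mantel-Haenszel, continuity-corrected | as above | 0.055 |
| SAP pooling with Hartung-Knapp, 1 df | 3.72 | 0.32 |

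For the Cochran-Mantel-Haenszel rows: observed XenMatrix events 15, expected 7.826 + 3.200 = 11.026, variance 2.057 + 1.213 = 3.269. Then χ² = 3.974²/3.269 = 4.83, or 3.474²/3.269 = 3.69 with the correction.

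**The case against.** The strongest reply is that the SAP's statement is accurate for the method it names, and that nothing printed is contradictory. In all four study rows the interval and the P value fall on the same side of the null. Table 3a also prints a non-Wald test for the randomised counts (Pearson P = 0.03). All of this stands, and it limits the mixed rows to a reporting fault.

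Other readings a reader might infer go further than the documents allow:
- **That printing profile intervals produced the P of 0.070.** It did not. The pooling never uses those intervals. Nor is the Wald test alone responsible: the one-stage model gives 0.031 by Wald. The main difference is two-stage against one-stage pooling. The random-effects term adds little (0.066 without it).
- **That the weighting short-changes the trial.** The SAP's unadjusted weights are 42% randomised and 58% observational. Mantel-Haenszel weights are 19 × 1/46 = 0.41 and 4 × 4/20 = 0.80, so that method gives the cohort even more, about 66%. In the adjusted pool the back-calculated standard errors give the trial 59%.
- **That the whole contrast between unadjusted and adjusted results is a Wald artefact.** The odds ratio rises from 3.72 to 12.48, and 12.48/4.09 is still about threefold if the one-stage estimate replaces 3.72.
- **That the unadjusted effect is now established.** The exact lower limit is 1.007, the corrected Cochran-Mantel-Haenszel P is 0.055 and Hartung-Knapp gives 0.32.

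There is also a fair warning about the remedy. In 40,000 simulated null datasets with these arm sizes and event rates of 12/46 and 8/20, the likelihood-ratio test rejected about 5.7% of the time, against about 3% for the SAP's method. Changing the test after the results are known, in the direction of significance, would itself be open to criticism.

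**Conclusion.** The point holds in a limited form and is worth correcting, though it is not critical. The mix of profile intervals and Wald P values is established by exact reproduction in the unadjusted table and inferred in the adjusted one. The unadjusted pooled P runs from 0.021 to 0.070 across the Wald, likelihood, exact and Mantel-Haenszel analyses, and reaches 0.32 with Hartung-Knapp. The right description is borderline and method-dependent.

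The confounding inference fails on two counts. Its premise depends on the pooling method, and a change in significance would not demonstrate confounding in any case. The rise in the odds ratio is a separate observation, which the Wald approximation does not explain and which cannot be examined further without patient-level data.

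The stratified, conditional and exact results assume a common odds ratio across the two sources. The random-slope model relaxes this and gives 0.032, but two studies say little about heterogeneity. Nothing here shows that the adjusted pooled result (P = 0.012) would change, and the check does not address whether randomised and non-randomised patients should be pooled.

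**What to change.** 1. In both results tables, take each row's P value and interval from the same method (likelihood-ratio with profile likelihood, or the Firth-penalised equivalents), and name the method in a footnote.
2. Under Primary Outcome Analysis, state which standard errors enter the pooling. Report a one-stage logistic model with study-specific intercepts alongside the two-stage result, unadjusted and adjusted, labelled post hoc.
3. In the Executive Summary, replace the flat statement of non-significance with a description of the unadjusted pooled result as borderline and dependent on method, and give the range.
4. Delete the sentence that infers confounding from the change in significance. If the change in the odds ratio is discussed, discuss it as a change in the estimate.

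The cost is one short re-run on data already held, plus wording. The one-stage likelihood-ratio test may slightly exceed its nominal 5% at these sample sizes, so its P value must stand beside the SAP's 0.070 and not replace it as the preferred answer.

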Range		0.00–9.00	0.00–6.00	
Mean±SD		2.69±2.73	1.43±1.61	
History of mesh repair : Yes	46	12/16 (75.00)	17/30 (56.67)	$\chi^2_1=1.51$, $P=0.22^2$
Hernia width	41			$F_{1,39}=2.14$, $P=0.15^3$
N		16	25	
Median (interquartile range)		15.80 (9.95–18.71)	12.60 (9.20–14.80)	
Range		2.10–30.30	2.20–22.20	
Mean±SD		14.91±7.41	11.67±5.48	
Hernia width (imputed)	46			$F_{1,44}=0.68$, $P=0.41^3$
N		16	30	
Median (interquartile range)		15.80 (9.95–18.71)	12.90 (9.48–18.65)	
Range		2.10–30.30	2.20–30.00	
Mean±SD		14.91±7.41	13.06±6.46	
Hernia length	41			$F_{1,39}=0.10$, $P=0.75^3$
N		16	25	
Median (interquartile range)		16.60 (9.84–20.00)	11.80 (8.20–21.60)	
Range		2.30–28.00	3.50–27.70	
Mean±SD		15.30±6.90	14.20±7.89	
Hernia length (imputed)	46			$F_{1,44}=0.01$, $P=0.93^3$
N		16	30	
Median (interquartile range)		16.60 (9.84–20.00)	16.25 (9.00–21.41)	
Range		2.30–28.00	3.50–27.70	
Mean±SD		15.30±6.90	15.05±7.49	
Hernia area	41			$F_{1,39}=1.33$, $P=0.26^3$
N		16	25	
Median (interquartile range)		275.97 (96.08–354.27)	153.40 (45.61–301.15)	
Range		8.61–700.00	7.70–545.69	
Mean±SD		265.97±200.88	195.61±157.45	
Total OR time (min)	43			$F_{1,41}=0.29$, $P=0.59^3$
N		14	29	
Median (interquartile range)		471.50 (443.50–483.58)	417.00 (336.33–547.67)	
Range		292.00–560.00	212.00–838.00	
Mean±SD		462.57±58.22	451.17±142.81	
ASA class	46			$\chi^2_2=2.21$, $P=0.33^2$
2		3/16 (18.75)	3/30 (10.00)	
3		13/16 (81.25)	24/30 (80.00)	

Table 1a: Baseline demographics, randomized patients (*continued*)

Variables	N	Strattice	XenMatrix	Test Statistic
4		0/16 (0.00)	3/30 (10.00)	

Note:

N is the number of non-missing value. 1 Kruskal-Wallis. 2 Pearson. 3 Wilcoxon.

Stat, P is the test statistic and p-value.

cata = check all that apply

Table 1b: Baseline demographics, observational patients

Variables	N	Strattice	XenMatrix	Test Statistic
Gender : Male	20	(N=12) 6/12 (50.00)	(N=8) 3/8 (37.50)	$\chi^2_1=0.30$, $P=0.58^2$
Days from surgery to last follow-up	20	N 12	8	$F_{1,18}=1.18$, $P=0.29^3$
Median (interquartile range)		311.50 (93.67–469.17)	570.50 (156.75–1293.50)	
Range		54.00–855.00	64.00–1751.00	
Mean±SD		327.08±266.89	715.38±669.49	
Age	20			$F_{1,18}=0.01$, $P=0.94^3$
N		12	8	
Median (interquartile range)		55.00 (49.42–60.58)	57.50 (35.33–67.58)	
Range		32.00–70.00	30.00–73.00	
Mean±SD		54.75±10.16	53.12±17.01	
Body mass index	20			$F_{1,18}=2.30$, $P=0.15^3$
N		12	8	
Median (interquartile range)		36.48 (32.12–38.26)	32.97 (25.34–35.71)	
Range		24.17–47.60	21.49–39.67	
Mean±SD		35.59±6.02	31.23±6.49	
BMI >30kg/m ² : Yes	20	10/12 (83.33)	5/8 (62.50)	$\chi^2_1=1.11$, $P=0.29^2$
Diabetes : Yes	20	2/12 (16.67)	0/8 (0.00)	$\chi^2_1=1.48$, $P=0.22^2$
Hypertension : Yes	20	7/12 (58.33)	2/8 (25.00)	$\chi^2_1=2.15$, $P=0.14^2$
COPD : Yes	20	1/12 (8.33)	1/8 (12.50)	$\chi^2_1=0.09$, $P=0.76^2$
Immunosuppression : Yes	20	4/12 (33.33)	0/8 (0.00)	$\chi^2_1=3.33$, $P=0.07^2$
Primary hernia diagnosis : Yes	20	4/12 (33.33)	7/8 (87.50)	$\chi^2_1=5.69$, $P=0.02^2$
Previous repair : Yes	20	7/12 (58.33)	3/8 (37.50)	$\chi^2_1=0.83$, $P=0.36^2$
Number of prior hernia repairs	20			$F_{1,18}=0.33$, $P=0.57^3$
N		12	8	
Median (interquartile range)		1.00 (0.00–1.58)	0.00 (0.00–2.17)	
Range		0.00–9.00	0.00–6.00	
Mean±SD		1.50±2.54	1.25±2.19	
History of mesh repair : Yes	20	6/12 (50.00)	3/8 (37.50)	$\chi^2_1=0.30$, $P=0.58^2$
Hernia width	19			$F_{1,17}=5.27$, $P=0.03^3$
N		11	8	
Median (interquartile range)		11.70 (9.75–16.47)	16.50 (15.27–19.93)	
Range		2.80–30.00	15.00–22.50	
Mean±SD		13.23±7.78	17.54±2.94	
Hernia width (imputed)	20			$F_{1,18}=2.89$, $P=0.11^3$
N		12	8	
Median (interquartile range)		12.45 (9.82–20.15)	16.50 (15.27–19.93)	
Range		2.80–30.00	15.00–22.50	
Mean±SD		14.62±8.86	17.54±2.94	
Hernia length	19			$F_{1,17}=0.01$, $P=0.91^3$
N		11	8	
Median (interquartile range)		22.50 (20.10–25.08)	22.35 (19.17–27.41)	
Range		2.40–32.70	13.50–30.00	
Mean±SD		20.27±9.01	22.61±5.47	
Hernia length (imputed)	20			$F_{1,18}=0.07$, $P=0.80^3$
N		12	8	
Median (interquartile range)		22.05 (20.00–24.91)	22.35 (19.17–27.41)	
Range		2.40–32.70	13.50–30.00	
Mean±SD		20.25±8.59	22.61±5.47	
Hernia area	19			$F_{1,17}=2.69$, $P=0.12^3$
N		11	8	
Median (interquartile range)		284.28 (231.27–422.23)	362.85 (322.09–467.22)	
Range		6.72–600.00	230.90–657.00	
Mean±SD		298.77±188.98	398.54±130.54	

Table 1b: Baseline demographics, observational patients (continued)

Variables	N	Strattice	XenMatrix	Test Statistic
Total OR time (min)	19			$F_{1,17}=0.34, P=0.57^3$
N	12	7		
Median (interquartile range)	431.00 (383.17–540.58)	551.00 (345.17–575.83)		
Range	310.00–696.00	289.00–1018.00		
Mean±SD	465.08±117.42	538.86±240.86		
ASA class	20			$\chi^2=3.59, P=0.17^2$
2	1/12 (8.33)	1/8 (12.50)		
3	11/12 (91.67)	5/8 (62.50)		
4	0/12 (0.00)	2/8 (25.00)		

Note:

N is the number of non-missing value. 1 Kruskal-Wallis. 2 Pearson. 3 Wilcoxon.

Stat, P is the test statistic and p-value.

cata = check all that apply

Surgical Characteristics

Table 2a: Surgical demographics, randomized patients

Variables	N	Strattice (N=16)	XenMatrix (N=30)	Test Statistic
Types of hernia diagnosis ^{cata}				
Ventral hernia : Yes	46	15/16 (93.75)	28/30 (93.33)	$\chi^2_1=0.00, P=0.96^2$
Flank hernia : Yes	46	0/16 (0.00)	2/30 (6.67)	$\chi^2_1=1.12, P=0.29^2$
Parastomal hernia : Yes	46	3/16 (18.75)	3/30 (10.00)	$\chi^2_1=0.70, P=0.40^2$
Umbilical hernia : Yes	46	0/16 (0.00)	0/30 (0.00)	NA
Parastomal hernia : Yes	46	3/16 (18.75)	3/30 (10.00)	$\chi^2_1=0.70, P=0.40^2$
CDC wound class	46			$\chi^2_3=3.08, P=0.38^2$
1		7/16 (43.75)	17/30 (56.67)	
2		5/16 (31.25)	4/30 (13.33)	
3		2/16 (12.50)	2/30 (6.67)	
4		2/16 (12.50)	7/30 (23.33)	
VHWG grade	46			$\chi^2_3=3.46, P=0.33^2$
1		1/16 (6.25)	1/30 (3.33)	
2		2/16 (12.50)	9/30 (30.00)	
3		11/16 (68.75)	13/30 (43.33)	
4		2/16 (12.50)	7/30 (23.33)	
Kanters grade	46			$\chi^2_2=1.12, P=0.57^2$
1		1/16 (6.25)	1/30 (3.33)	
2		6/16 (37.50)	16/30 (53.33)	
3		9/16 (56.25)	13/30 (43.33)	
Primary fascial repair : Yes	46	14/16 (87.50)	22/30 (73.33)	$\chi^2_1=1.23, P=0.27^2$
Unilateral component separation : Yes	46	2/16 (12.50)	2/30 (6.67)	$\chi^2_1=0.45, P=0.50^2$
Bilateral component separation : Yes	46	8/16 (50.00)	17/30 (56.67)	$\chi^2_1=0.19, P=0.67^2$
Bridged repair : Yes	46	2/16 (12.50)	6/30 (20.00)	$\chi^2_1=0.41, P=0.52^2$
Mesh position ^{cata}				
Onlay mesh placement : Yes	46	0/16 (0.00)	3/30 (10.00)	$\chi^2_1=1.71, P=0.19^2$
Underlay mesh placement : Yes	46	12/16 (75.00)	24/30 (80.00)	$\chi^2_1=0.15, P=0.70^2$
Inlay mesh placement : Yes	46	0/16 (0.00)	2/30 (6.67)	$\chi^2_1=1.12, P=0.29^2$
Sublay mesh placement : Yes	46	4/16 (25.00)	8/30 (26.67)	$\chi^2_1=0.02, P=0.90^2$

Note:

N is the number of non-missing value. 1 Kruskal-Wallis. 2 Pearson. 3 Wilcoxon.

Stat, P is the test statistic and p-value.

cata = check all that apply

Table 2b: Surgical demographics, observational patients

Variables	N	Strattice (N=12)	XenMatrix (N=8)	Test Statistic
Types of hernia diagnosis ^{cata}				
Ventral hernia : Yes	20	11/12 (91.67)	7/8 (87.50)	$\chi^2_1=0.09, P=0.76^2$
Flank hernia : Yes	20	2/12 (16.67)	1/8 (12.50)	$\chi^2_1=0.07, P=0.80^2$
Parastomal hernia : Yes	20	4/12 (33.33)	0/8 (0.00)	$\chi^2_1=3.33, P=0.07^2$

Table 2b: Surgical demographics, observational patients (continued)

Variables	N	Strattice	XenMatrix	Test Statistic
Umbilical hernia : Yes	20	0/12 (0.00)	0/8 (0.00)	NA
Parastomal hernia : Yes	20	4/12 (33.33)	0/8 (0.00)	$\chi^2_1=3.33, P=0.07^2$
CDC wound class	20			$\chi^2_3=3.64, P=0.30^2$
1		6/12 (50.00)	5/8 (62.50)	
2		3/12 (25.00)	2/8 (25.00)	
3		0/12 (0.00)	1/8 (12.50)	
4		3/12 (25.00)	0/8 (0.00)	
VHWG grade	20			$\chi^2_3=4.49, P=0.21^2$
1		0/12 (0.00)	1/8 (12.50)	
2		6/12 (50.00)	2/8 (25.00)	
3		4/12 (33.33)	5/8 (62.50)	
4		2/12 (16.67)	0/8 (0.00)	
Kanters grade	20			$\chi^2_1=0.83, P=0.36^2$
1		0/12 (0.00)	0/8 (0.00)	
2		5/12 (41.67)	5/8 (62.50)	
3		7/12 (58.33)	3/8 (37.50)	
Primary fascial repair : Yes	19	9/12 (75.00)	6/7 (85.71)	$\chi^2_1=0.31, P=0.58^2$
Unilateral component separation : Yes	20	1/12 (8.33)	0/8 (0.00)	$\chi^2_1=0.70, P=0.40^2$
Bilateral component separation : Yes	20	4/12 (33.33)	7/8 (87.50)	$\chi^2_1=5.69, P=0.02^2$
Bridged repair : Yes	19	4/12 (33.33)	1/7 (14.29)	$\chi^2_1=0.83, P=0.36^2$
Mesh position ^{cata}				
Onlay mesh placement : Yes	20	0/12 (0.00)	0/8 (0.00)	NA
Underlay mesh placement : Yes	20	12/12 (100.00)	6/8 (75.00)	$\chi^2_1=3.33, P=0.07^2$
Inlay mesh placement : Yes	20	1/12 (8.33)	1/8 (12.50)	$\chi^2_1=0.09, P=0.76^2$
Sublay mesh placement : Yes	20	0/12 (0.00)	2/8 (25.00)	$\chi^2_1=3.33, P=0.07^2$

Note:

N is the number of non-missing value. 1 Kruskal-Wallis. 2 Pearson. 3 Wilcoxon.

Stat, P is the test statistic and p-value.

cata = check all that apply

6-week Outcomes

Table 3a: 6-week outcomes, randomized patients

Variables	N	Strattice	XenMatrix	Test Statistic
		(N=16)	(N=30)	
Bulge : Yes	46	0/16 (0.00)	0/30 (0.00)	NA
Recurrence : Yes	46	0/16 (0.00)	0/30 (0.00)	NA
SSO within 6 weeks : Yes	46	1/16 (6.25)	11/30 (36.67)	$\chi^2_1=5.01, P=0.03^2$
SSO Type (cata)				
Skin necrosis : Yes	46	0/16 (0.00)	1/30 (3.33)	$\chi^2_1=0.55, P=0.46^2$
Enterocutaneous fistula : Yes	46	0/16 (0.00)	2/30 (6.67)	$\chi^2_1=1.12, P=0.29^2$
Dehiscence : Yes	46	0/16 (0.00)	1/30 (3.33)	$\chi^2_1=0.55, P=0.46^2$
Seroma : Yes	46	0/16 (0.00)	2/30 (6.67)	$\chi^2_1=1.12, P=0.29^2$
Hematoma : Yes	46	0/16 (0.00)	0/30 (0.00)	NA
Infection : Yes	46	1/16 (6.25)	10/30 (33.33)	$\chi^2_1=4.21, P=0.04^2$
Mesh infection : Yes	46	0/16 (0.00)	3/30 (10.00)	$\chi^2_1=1.71, P=0.19^2$

Note:

N is the number of non-missing value. 1 Kruskal-Wallis. 2 Pearson. 3 Wilcoxon.

Stat, P is the test statistic and p-value.

cata = check all that apply

Table 3b: 6-week outcomes, observational patients

Variables	N	Strattice	XenMatrix	Test Statistic
		(N=12)	(N=8)	
Bulge : Yes	20	0/12 (0.00)	0/8 (0.00)	NA
Recurrence : Yes	20	1/12 (8.33)	0/8 (0.00)	$\chi^2_1=0.70, P=0.40^2$
SSO within 6 weeks : Yes	20	4/12 (33.33)	4/8 (50.00)	$\chi^2_1=0.56, P=0.46^2$
SSO Type (cata)				
Skin necrosis : Yes	20	0/12 (0.00)	1/8 (12.50)	$\chi^2_1=1.58, P=0.21^2$
Enterocutaneous fistula : Yes	20	2/12 (16.67)	0/8 (0.00)	$\chi^2_1=1.48, P=0.22^2$

Table 3b: 6-week outcomes, observational patients (*continued*)

Variables	N	Strattice	XenMatrix	Test Statistic
Dehiscence : Yes	20	2/12 (16.67)	0/8 (0.00)	$\chi^2_1=1.48$, P=0.22 ²
Seroma : Yes	20	1/12 (8.33)	0/8 (0.00)	$\chi^2_1=0.70$, P=0.40 ²
Hematoma : Yes	20	0/12 (0.00)	0/8 (0.00)	NA
Infection : Yes	20	1/12 (8.33)	3/8 (37.50)	$\chi^2_1=2.55$, P=0.11 ²
Mesh infection : Yes	19	0/11 (0.00)	0/8 (0.00)	NA

Note:

N is the number of non-missing value. 1 Kruskal-Wallis. 2 Pearson. 3 Wilcoxon.

Stat, P is the test statistic and p-value.

cata = check all that apply

Results

Executive Summary

Unadjusted Random Effects Meta-Analysis (Simple Logistic Regression):

Effect Estimate (Odds Ratio): 3.718 (0.897, 15.404)

Significance: The pooled estimate was not statistically significant.

Heterogeneity:

I^2 (total heterogeneity / total variability): 3.29%

H^2 (total variability / sampling variability): 1.03

Test for Heterogeneity:

$Q(df = 1) = 1.0340$, $p\text{-val} = 0.3092$

There appears to be minimal variability between the two studies. The I^2 value of 3.29% indicates that nearly all of the total variation can be explained by chance rather than true heterogeneity, and an H^2 of 1.03 reflects low excess variability. The Q test ($Q = 1.034$, $p = 0.3092$) is nonsignificant, confirming that there is no strong evidence of meaningful heterogeneity.

Adjusted Random Effects Meta-Analysis (Multivariable Logistic Regression):

Effect Estimate (Odds Ratio): 12.476 (1.745, 89.199)

Significance: The pooled estimate was statistically significant.

Heterogeneity:

I^2 (total heterogeneity / total variability): 0.00%

H^2 (total variability / sampling variability): 1.00

Test for Heterogeneity: $Q(df = 1) = 0.2830$, $p\text{-val} = 0.5947$

There is effectively no evidence of meaningful heterogeneity between the RCT and the observational study, provided by 0.00% I^2 value. Similarly, $H^2 = 1.00$ supports the absence of excess variability beyond what would be expected by sampling error alone. Finally, the Q test ($Q = 0.2830$, $p = 0.5947$) is non-significant, confirming that the studies are consistent and do not exhibit statistically detectable heterogeneity.

When covariates were included in the model, a previously non-significant association between the exposure and outcome became statistically significant. This shift suggests that the unadjusted analysis may have been confounded—i.e., certain variables were masking or biasing the relationship.

Note

Be wary of exaggerated findings, as smaller studies are more prone to exaggeration. This is known as a Type M (magnitude) error. In other words, a finding must be large enough to exceed the statistical significance threshold despite wide confidence intervals, which systematically inflates the estimated effect size. Consequently, although we observed a strong effect, its true magnitude may be substantially lower than our point estimate suggests.

Gelman, A., & Carlin, J. (2014). Beyond Power Calculations: Assessing Type S (Sign) and Type M (Magnitude) Errors. *Perspectives on Psychological Science*, 9(6), 641-651.

[figure not shown]
Random Effects Meta-Analysis: Simple Logistic Regression

Simple logistic regression = logistic regression with no adjustment for confounders

[figure not shown]
Random Effects Meta-Analysis: Simple Logistic Regression

Study	Estimate (log OR)	95% CI (log OR)	Estimate (OR)	95% CI (OR)	P-value
Randomized	2.162	(0.365, 5.123)	8.684	(1.441, 167.853)	0.049
Observational	0.693	(-1.143, 2.597)	2.000	(0.319, 13.423)	0.459
RE Meta-Analysis	1.313	(-0.108, 2.735)	3.718	(0.897, 15.404)	0.070

Forest Plot: Log Odds Scale

Forest Plot: Odds Scale

[figure not shown]

Random Effects Meta-Analysis: Multivariable logistic regression

[figure not shown]
Random Effects Meta-Analysis: Multivariable Logistic Regression

Study	Estimate (log OR)	95% CI (log OR)	Estimate (OR)	95% CI (OR)	P-value
Randomized	2.968	(0.815, 6.261)	19.458	(2.258, 523.717)	0.023
Observational	1.882	(-0.898, 5.783)	6.569	(0.407, 324.629)	0.230
RE Meta-Analysis	2.524	(0.557, 4.491)	12.476	(1.745, 89.199)	0.012

Log Odds Scale

Odds Scale

FAQ

Q: What is overfitting?

A: Overfitting in regression happens when a model is too complex, often due to too many parameters relative to a small sample size, causing it to capture noise rather than the true data pattern. With limited data, the model lacks sufficient information to generalize well, leading to poor performance on new data because it is overly tailored to the specific quirks of the training set.

Q: What is a chunk (or composite) test?

A: A chunk or composite hypothesis test is often used for categorical variables to assess whether the entire variable contributes significantly to the model, rather than just specific categories. By testing all categories together, this approach helps determine if the variable as a whole has an effect, rather than focusing on individual category differences alone.

Q: What can I say when I have a large p-value?

A. This is a friendly reminder that absence of evidence does not mean evidence of absence. A large p-value doesn't prove there is no effect; it simply indicates that we don't have strong evidence to detect a difference. Instead of incorrectly concluding "there were no differences," it's more accurate to say, "there was no evidence of a difference." Additionally, you can use the confidence interval to provide more context. For example, if comparing complication rates, and the confidence interval suggests the difference could be as much as ± 5 percentage points, you might say: "If there is a difference between procedure A and procedure B, it is likely no larger than 5 percentage points." Similarly, for odds ratios, if the confidence interval includes a range up to 2, you could say, "There may be at most a 100% increase in odds or up to a 50% decrease in odds." This acknowledges uncertainty without overinterpreting the results.

Answer generously borrowed and adapted from this blog post([link](#)) by [name].

Also see this article for explanation of interpretation of evidence and suggestions about communicating levels of evidence.

Q. What is validation and optimism-corrected statistics?

A. When a model is fit to a dataset, it tends to perform better on that dataset than it would on new, unseen data, leading to overly optimistic predictions and performance statistics. To adjust for this, techniques like cross-validation or bootstrapping are used to correct for this optimism, producing "optimism-corrected" statistics, which provide a more realistic estimate of the model's performance on future data. These corrections help ensure that the model's results are not overly tailored to the training data and are more generalizable.

Q. What are Brier scores (B)?

A. The Brier score measures how well a model predicts binary or categorical outcomes by calculating the mean squared difference between the predicted probabilities and the actual outcomes. It ranges from 0 to 1, with lower scores indicating better predictive accuracy and calibration. A Brier score closer to 0 suggests that the model's predicted probabilities align well with the observed outcomes, making it a useful metric for evaluating the accuracy of probabilistic predictions.

Q. What is the g-index (g)?

A. The g-index measures the ability of a model to discriminate between outcomes based on the Gini mean difference, reflecting the typical difference between predictions for any two randomly selected individuals. In essence, a higher g-index indicates better discrimination, meaning the model provides a wider range of predictions that can distinguish between individuals more effectively. For example, in a time-to-event analysis, a larger g-index suggests that the model can predict meaningful differences in survival times or hazard rates between patients.

For time-to-event outcomes: A higher g-index indicates larger differences in predicted log relative hazards between patients, which implies better discrimination. For binary/ordinal outcomes: The g-index reflects the typical log odds ratio between predictions for any two patients, meaning how much their odds of an outcome differ. For continuous outcomes: The g-index represents the typical difference in predicted values, showing how far apart predictions are for different patients. Overall, a higher g-index means the model is better at distinguishing between individuals based on their predicted outcomes.

Here are improved explanations for each of your questions:

Q. What is validation and optimism-corrected statistics?

A. When a model is fit to a dataset, it tends to perform better on that dataset than it would on new, unseen data, leading to overly optimistic predictions and performance statistics. To adjust for this, techniques like cross-validation or bootstrapping are used to correct for this optimism, producing "optimism-corrected" statistics, which provide a more realistic estimate of the model's performance on future data. These corrections help ensure that the model's results are not overly tailored to the training data and are more generalizable.

Q. What are Brier scores (B)?

A. The Brier score measures how well a model predicts binary or categorical outcomes by calculating the mean squared difference between the predicted probabilities and the actual outcomes. It ranges from 0 to 1, with lower scores indicating better predictive accuracy and calibration. A Brier score closer to 0 suggests that the model's predicted probabilities align well with the observed outcomes, making it a useful metric for evaluating the accuracy of probabilistic predictions.

Q. What is the g-index (g)?

A. The g-index measures the ability of a model to discriminate between outcomes based on the Gini mean difference, reflecting the typical difference between predictions for any two randomly selected individuals. In essence, a higher g-index indicates better discrimination, meaning the model provides a wider range of predictions that can distinguish between individuals more effectively. For example, in a time-to-event analysis, a larger g-index suggests that the model can predict meaningful differences in survival times or hazard rates between patients.

For time-to-event outcomes: A higher g-index indicates larger differences in predicted log relative hazards between patients, which implies better discrimination. For binary/ordinal outcomes: The g-index reflects the typical log odds ratio between predictions for any two patients, meaning how much their odds of an outcome differ. For continuous outcomes: The g-index represents the typical difference in predicted values, showing how far apart predictions are for different patients. Overall, a higher g-index means the model is better at distinguishing between individuals based on their predicted outcomes.

g is on the original scale gr is on the ratio scale (e.g. odds/hazard) gp is on the probability or risk scale

Q. What is DXY?

A. Dxy, or Somers' Dxy, is a statistic used to measure a model's discrimination ability, which refers to how well the model can distinguish between different outcomes. Dxy ranges from -1 to 1, with 1 indicating perfect discrimination and 0 indicating no better than random guessing. For binary outcomes, Dxy is related to the concordance index (c-index) and can be expressed as $Dxy = 2 * (c\text{-index} - 0.5)$. In time-to-event models, Dxy represents the rank correlation between the predicted log relative hazard and observed survival times, similar to a rank-based R2. Higher Dxy values indicate that the model does a better job at ranking individuals according to their predicted outcomes.

For example:

$Dxy = 0.5$ means 75% of pairs are concordant (the predictions are in the correct order), and 25% are discordant. $Dxy = 0.2$ means 60% of pairs are concordant, and 40% are discordant. According to [name], there are no universally "acceptable" values for Dxy, as the significance depends on the difficulty of predicting the specific outcome (e.g., lower values may still be informative for difficult-to-predict outcomes like mortality).

Q. What is a restricted cubic spline? What are knots?

A. Restricted cubic splines are a flexible tool used in statistical models to better capture non-linear relationships between a continuous variable and an outcome. Instead of assuming a straight-line relationship, restricted cubic splines break the data into sections at specific points, called “knots,” and fit smooth curves between them. The “restricted” part means the curves become straight lines at the ends, ensuring the model doesn’t overreact to extreme values. This method helps create a smoother, more realistic fit to the data without making the model too complicated or unstable, making it useful when simple linear relationships aren’t sufficient.

Q. What is a tipping point analysis?

